Cerebral Performance Category (CPC) and Cerebral Performance Category-Extended (CPC-E) score assessments: CPC and CPC-E will be assessed just prior to hospital discharge, at 30 and 90 days. Research staff will approach patients for assessment of CPC-E prior to hospital discharge. The CPC-E includes several questions testing logical thinking, attention and memory. The outpatient portion, which will be assessed in addition to the inpatient portion after hospital discharge/at 30 and 90 days, also includes questions about functional status and return to work. The CPC score will also be assessed by research staff prior to discharge. Phone calls to the patient will be made at 30 and 90 days (if the patient is no longer in the hospital).

Outcome Measures

Primary Outcome: Lactate change

The primary outcome is change in lactate over 24 hours following enrollment.

Secondary Outcomes:

1. Absolute level and change in VO₂ over 48 hours
2. Absolute level of lactate over 72 hours
3. Absolute level and the change in pyruvate dehydrogenase (PDH) quantity, activity and specific activity over 72 hours
4. Absolute level and the change in S100 levels over 72 hours
5. Absolute level and the change in neuron-specific enolase (NSE) levels over 72 hours
6. Mortality (hospital discharge, 30 and 90 days)
7. Cerebral Performance Category (CPC) score (hospital discharge, 30 and 90 days)
8. Cerebral Performance Category-Extended (CPC-E) (hospital discharge, 30 and 90 days)
9. Absolute level and the change in Sequential Organ Failure Assessment (SOFA) Score SOFA over 72 hours
10. Acute renal failure during first 7 days following arrest
11. Absolute level and change in cellular oxygen consumption rate over 72 hours
12. Absolute level and the change in creatinine over 72 hours

Sample Size Calculations:

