The analysis method for the primary endpoint will be linear mixed-effects modeling (LMM). This type of modeling is used in longitudinal or repeated-measures studies to take into account the correlation of within-subject measurements and can optimize the power. In this case, each subject will have lactate measurements at multiple time points, which are correlated. Since LMM will be used for the analysis, we have also used LMM for power analysis for this endpoint. We evaluated approximately 61 post-arrest patients in our databases for which we had lactate measurements over 24 hours and that matched the inclusion/exclusion criteria for the current proposal. We observed that the post-CA patients have a mean lactate of 3.8 ± 2.2 mmol/L at 6 hours, 3.5 ± 2.2 at 12-hours, and 2.9 ± 2 at 24-hours. We took a conservative position to assume that the potential effect size (the mean difference of lactate between the two groups) will be 33%. That is, we assumed that the mean lactate level at the three different time points were 2.55, 2.35, and 1.94. We then simulated the longitudinal data with the assumption that the variance-covariance structure of the lactate data followed a compound-symmetry structure with between-subject variance of 2.07. The linear-mixed effects model was used on the simulated data to obtain the estimated F statistic, numerator, and denominator degrees of freedom. From these estimates, the non-centrality parameter was computed and used to obtain the power. To obtain 80% power, with type-I error of 0.05, 66 subjects (33 thiamine, 33 placebo) will be needed to detect the stated difference over 6, 12, and 24-hours. We

secondarily performed calculations using the difference in means approach at the time point of 6 hours where we anticipate maximal effect of thiamine. At this time point, a reduction by 33% yields a power of 80% with a total sample size of 92. To be conservative we will use the larger sample size of 92 patients to ensure adequate power. With this sample size, the linear-mixed model will have 92% power to detect differences between groups with the same assumptions.

Statistical Analysis

General Principles

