The statistical analyses and reporting will adhere to the CONSORT guidelines. All tests will be two-sided, a p-value <0.05 will be considered significant, and all confidence intervals will have 95% coverage. All analyses will be conducted on a modified intention-to-treat basis only including participants receiving at least the first dose of the study medication. In a double-blind trial, this approach is unbiased while increasing precision. Analyses will not be adjusted for covariates unless there are significant differences in baseline characteristics between study arms.

Baseline Characteristics

A description of the baseline characteristics will be presented by treatment arm. Categorical variables will be summarized by frequencies and percentages. Percentages will be calculated according to the number of patients for whom data are available. Continuous variables will be summarized using mean+/-standard deviation or median (interquartile range) based on the distribution of the data.

Analysis of Primary Outcome

We will compare repeated measures of lactate levels at each time point (0h, 6h, 12h, 24h) between arms using a linear mixed-effects model with an independent variance-covariance matrix to account for the correlation of within-patient repeated measures. Covariates in the model include treatment arm, time (as a categorical variable with four levels, defined as baseline, 6 hours, 12 hours, and 24 hours), and the interaction between treatment arm and time. Linear contrasts will be used to estimate the mean difference between treatment arms for each time point. If a patient dies before 24 hours, levels will be imputed by carrying forward the last known value before the event with a 20% penalty. A sensitivity analysis will be performed in which patients who die before 24 hours are assigned the last known value before the event without a penalty.

Analysis of Secondary Outcomes

Lactate levels over 72 hours

To test for a difference in absolute lactate level values, we will compare means or medians, as appropriate, between arms using either a Student's t-test or a Wilcoxon rank-sum test, respectively, at 6, 12, 24 and 72 hours.

Change in oxygen consumption (VO₂) over 48 hours

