To investigate the association between treatment and gas metabolism data (VO₂, VCO₂ and RQ) in the first 48 hours after ROSC, we will compare the area under the curve (AUC) for each oxygen consumption variable between the treatment arms. The AUCs for the oxygen consumption variables are influenced by the number of minutes of data available, which varies between patients. To account for this, AUCs for each patient will be adjusted by dividing by the number of minutes of oxygen consumption data available for that patient. Additionally, the AUCs for the VO₂ and VCO₂ variables are influenced by the weight of the patient, and thus will also be adjusted by dividing by the bodyweight of the patient, in kilograms. The median AUCs will be compared between treatment groups using the univariate Wilcoxon rank-sum test. To

control for the known effect of temperature on oxygen consumption, we will use quantile regression to compare median AUCs between patients using the treatment assignment as the predictor and average temperature as a covariate. To examine the association between treatment and the VO₂:Lactate Ratio, we will use a linear quantile mixed model (LQMM) with the VO₂:Lactate Ratio as the outcome variable, treatment as the predictor variable and temperature as the covariate. To account for clustering of VO₂:Lactate Ratio and temperature measurements within patients, we will add a random intercept for each patient to the LQMM. We will not control for vasopressor use or sedation in the above analyses unless use of these agents is significantly imbalanced between arms.

Pyruvate dehydrogenase (PDH), S100, NSE, SOFA score, creatinine, and cellular oxygen consumption rate levels over 72 hours

To test change over time, we will compare repeated measures of each outcome listed above at each time point (0h, 24h, 72h) between arms using a linear mixed-effects model with an independent variance–covariance matrix to account for the correlation of within-patient repeated measures. Covariates in the model include treatment arm, time, and the interaction between treatment arm and time. Linear contrasts will be used to estimate the mean difference between treatment arms for each time point. To test for a difference in absolute values between arms, we will compare means or medians, as appropriate, using either a Student’s t-test or a Wilcoxon rank-sum test, respectively, at 24 and 72 hours.

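### The primary lactate model does not adjust for 0 h lactate, and an undefined baseline-significance rule decides any covariate adjustment: lost precision and an unfixed model, not bias

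*SAP*

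**What the plan says.** Under Statistical Analysis, General Principles, the SAP states: "Analyses will not be adjusted for covariates unless there are significant differences in baseline characteristics between study arms". The same paragraph sets the level for all tests: "a p-value <0.05 will be considered significant". It does not say which characteristics are compared, by which test, or which covariates enter the model if a difference is found. The Baseline Characteristics section is descriptive only: "A description of the baseline characteristics will be presented by treatment arm".

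Under Outcome Measures, "The primary outcome is change in lactate over 24 hours following enrollment". Analysis of Primary Outcome fits lactate at 0, 6, 12 and 24 h as the response, with arm, four-level time and their interaction, and then: "Linear contrasts will be used to estimate the mean difference between treatment arms for each time point". 0 h lactate is neither a covariate nor constrained to a common mean across arms. Its only other planned use is a subanalysis split at 5.

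The models for PDH, S100, NSE, SOFA, creatinine and cellular oxygen consumption have the same form: "we will compare repeated measures of each outcome listed above at each time point (0h, 24h, 72h) between arms".

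**The concern.** Blood for 0 h lactate is drawn before study drug, and a pre-dose measurement of the outcome is usually the strongest covariate at hand. Placing it on the response side with free arm means gives the per-time contrasts no adjustment. A chance 0 h difference that falls short of significance therefore stays in those contrasts. It does not stay in the change terms, but these subtract the whole 0 h value rather than the part that predicts later lactate.

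The rule in General Principles does not make up for this. Under randomisation any baseline difference is due to chance, so a significance test selects a few trials for adjustment and leaves the rest unadjusted. Because the rule is undefined, two analysts could reach different primary models from the same data. At stake are precision on the primary outcome and a model fixed in advance.

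**Working it through.** **Inputs from the SAP.** 92 patients, 1:1, so 46 per arm; two-sided 0.05; 6 h mean 3.8 with SD 2.2 against 2.55, a difference of 1.25.

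**Assumptions, not in the SAP.** Correlation r between 0 h and 6 h lactate from 0.2 to 0.6. 0 h SD s0 of 1.5, 2.2 or 3.0 (this matters only for change scores). The planning covariance "followed a compound-symmetry structure with between-subject variance of 2.07". Taking total variance (4.84 + 4.84 + 4.00)/3 = 4.56 gives r = 2.07/4.56 = 0.454, if that structure extends back to 0 h.

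**1. The plan's own figure.** SE = 2.2 × √(2/46) = 0.459 and 1.25/0.459 = 2.72, which gives 76.9% power by noncentral t. The SAP states 80% at 92; from its inputs, 80% needs 98 (normal approximation) or 100 (t). That mismatch is a separate matter. Here 77% is the unadjusted reference.

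**2. What the planned contrasts estimate.** Arm and time are saturated, so with complete data the fitted means are the cell means. A random-intercept fit to one simulated trial (true differences 0 at 0 h and −1.25 at 6 h) gave contrasts of 0.52 at 0 h and −1.08 at 6 h, identical to the raw differences, with SE 0.446. The change comparison is −1.08 − 0.52 = −1.60. Constraining the 0 h means to be equal gave −1.26 with SE 0.419.

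**3. Variances per patient at 6 h.**
- raw: 2.2² = 4.84
- change: 2.2² + s0² − 2r × 2.2 × s0
- adjusted: 2.2²(1 − r²)

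Change minus adjusted equals (s0 − 2.2r)². It is zero only where the regression slope on 0 h lactate is 1. Powers at 46 per arm:

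| r | adjusted variance | adjusted power, noncentral t / simulated | change power, s0 = 1.5 / 2.2 / 3.0 |
|---|---|---|---|
| 0.2 | 4.65 | 78.6% / 78.0% | 69.5% / 56.8% / 42.6% |
| 0.3 | 4.40 | 80.7% / 80.3% | 74.7% / 62.5% / 47.1% |
| 0.454 | 3.84 | 85.7% / 85.3% | 83.4% / 73.2% / 56.2% |
| 0.6 | 3.10 | 92.1% / 91.7% | 91.8% / 85.4% / 68.4% |

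Unadjusted power is 77% throughout.

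**4. The significance rule.** If only 0 h lactate is tested, the rule fires in 5% of trials. Simulated power is 77.0%, 77.2%, 77.7% and 78.2% at the four correlations. At 0.454 that is (77.7 − 76.9)/(85.3 − 76.9), about a tenth of the gain. If any of 10 independent characteristics triggers an adjustment that includes 0 h lactate, the rule fires in 1 − 0.95¹⁰ = 40% of trials and power at 0.454 is about 81%, some 40% of the gain. With 20 characteristics it fires in 64% and power is 82% to 83%. Type I error is 4.1% to 5.0% on the one-variable reading and 4.4% to 4.9% with 10 or 20 characteristics.

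**5. Average over 6, 12 and 24 h.** Mean effect (1.25 + 1.15 + 0.96)/3 = 1.12. Raw variance (4.56 + 2 × 2.07)/3 = 2.90; adjustment removes 4.56r². Simulated power is about 88% unadjusted against 89%, 92% and 97% adjusted at r = 0.2, 0.3 and 0.454. Higher r is left out, because 0 h would then predict later values better than they predict each other.

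**6. Deaths.** Steps 1 to 5 ignore the rule that "levels will be imputed by carrying forward the last known value before the event with a 20% penalty". With that penalty, equal deaths in both arms and an assumed 0 h mean of 5.0, 6 h power at r = 0.3 to 0.6 is 71% unadjusted against 75% to 88% adjusted if 10% die before 24 h, and 65% against 70% to 83% if 20% die. The gap remains.

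**The case against.** The strongest reply is that the primary outcome is change, 0 h lactate is in the model, and the arm-by-time terms test change while removing chance 0 h imbalance. That stands as a defence of validity. It does not settle efficiency: at a 0 h SD of 1.5 and correlation 0.6 the change comparison matches adjustment (92% each), but at SD 3.0 and correlation 0.454 it has 56% power against 86%. The SAP gives neither quantity.

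The gain may also be small. The entry rule of lactate at least 3 truncates the 0 h distribution and may lower the correlation; at 0.2 the gain is one or two points.

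A reader might infer more than the document supports:
- **That the rule biases the result or inflates type I error.** It does not; the test is at worst slightly conservative.
- **That the rule recovers almost nothing.** This holds for power only if 0 h lactate alone is tested. The SAP does not say so, and recovery is larger if several characteristics can trigger adjustment. Even on the one-variable reading, the estimator's true sampling variance gains about 28% of the possible reduction, though the reported SE barely shows it.
- **That the trial is underpowered for want of adjustment.** The 6 h calculation is secondary, its shortfall from 80% has another cause, and unadjusted power for the three-time average is about 88% before deaths.
- **That the similar imbalance rule for vasopressors and sedation in the VO₂ section removes a treatment effect.** That would need use measured after dosing, and the SAP does not state the timing.

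**Conclusion.** The point holds as lost efficiency and an unfixed model. With the SAP's 6 h inputs and 92 patients, always adjusting for 0 h lactate raises power from about 77% to about 78%, 80%, 86% and 92% at correlations of 0.2, 0.3, 0.454 and 0.6. The correlation is an assumption; 0.454 follows from the SAP's variances only if its planning structure extends to 0 h. Change-score power depends in addition on the unstated 0 h SD, so no single figure can be given for that comparison. The significance rule gives part of the gain, about a tenth on the narrowest reading and more on wider ones. Which part cannot be known, because the rule is not defined. The planned analysis remains valid. The change is worth making because it is nearly free and fixes the primary model before the data are seen.

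**What to change.** - Model lactate at 6, 12 and 24 h with 0 h lactate always a covariate, whatever the balance. Alternatively, keep 0 h as a response with one common mean for both arms. That version gains precision only through the modelled within-patient correlation, so state a covariance structure that includes it; Analysis of Primary Outcome at present calls the matrix independent.
- Do the same for the 0/24/72 h secondary models, each with its own 0 h value.
- Name any other baseline covariates in advance, and delete the clause that makes adjustment depend on significant baseline differences. Keep the baseline table descriptive.

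The cost is SAP wording and one model degree of freedom per covariate. No new data are needed.

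### The SAP names no deciding test for the primary outcome (lactate change), and the level contrasts it does name make no use of 0 h lactate by default

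*SAP*

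**What the plan says.** Outcome Measures: "The primary outcome is change in lactate over 24 hours following enrollment". Absolute lactate level over 72 hours is listed separately as a secondary outcome.

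Analysis of Primary Outcome: lactate at 0, 6, 12 and 24 h is the response, with arm, categorical time and arm-by-time as fixed effects. The section then says: "Linear contrasts will be used to estimate the mean difference between treatment arms for each time point". No test is singled out.

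General Principles: "All tests will be two-sided, a p-value <0.05 will be considered significant". On covariates: "Analyses will not be adjusted for covariates unless there are significant differences in baseline characteristics between study arms". This rule is general and does not mention 0 h lactate.

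Three other places bear on the reading:

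- The secondary lactate analysis has its own t-test or Wilcoxon test, introduced by "To test for a difference in absolute lactate level values".
- The section on PDH, S100, NSE and the other markers uses a parallel mixed model, introduced by "To test change over time, we will compare repeated measures of each outcome listed above at each time point".
- Sample Size Calculations says a mixed model was "used on the simulated data to obtain the estimated F statistic, numerator, and denominator degrees of freedom", and that 66 subjects "will be needed to detect the stated difference over 6, 12, and 24-hours". The tested effect and its degrees of freedom are not given, and 0 h data are not mentioned.

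**The concern.** The outcome is a change, the named contrasts are levels, and level is already a separate secondary outcome. A reader could take the deciding test to be the joint arm-by-time test, an averaged arm difference, the 0 to 24 h change, or one of the per-time differences. These can disagree on the same data and differ in power, so the choice should be fixed before unblinding.

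The covariate rule adds to this. In the stated model, with complete data, a per-time contrast is the difference between two arm means at that time, and 0 h lactate does not enter it. Whether 0 h lactate is adjusted for would then depend on a significance test between randomised arms. Prespecified adjustment needs no such trigger and uses a measurement already taken before study drug.

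**Working it through.** **Inputs from Sample Size Calculations.** Control means are 3.8, 3.5 and 2.9 (SD 2.2, 2.2 and 2.0) and thiamine means 2.55, 2.35 and 1.94, so the differences d are 1.25, 1.15 and 0.96, with mean 3.36/3 = 1.12. Covariance is compound symmetry with between-subject variance 2.07. There are 46 per arm and alpha is 0.05 two-sided.

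**Not given.** The plan states no residual variance and no 0 h mean, SD or correlation. Two assumptions bracket the residual variance:

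- A: total variance V equals a stated SD squared: 4.84, 4.00, or the average (4.84 + 4.84 + 4.00)/3 = 4.56. The correlation 2.07/V is then 0.43-0.52.
- B: the residual variance is solved so that the averaged-level test has 80% power at 33 per arm. This gives 1.464, V = 3.53, SD 1.88 (below the stated SDs) and correlation 0.59.

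Unless noted, 0 h is assumed to have the same variance and correlation as later times, with no arm difference at 0 h. Attrition and the penalised imputation for deaths are not modelled.

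**The plan's own figures (80% at N=66, 92% at N=92).** Under A with V = 4.84 or 4.56, the averaged-level test gives 73.6% or 74.9% at N=66, and 86.7% or 87.7% at N=92. Under B it gives 80% and 91.3%. Under B the joint arm-by-time test including 0 h gives 79.9% and 92.1%. The stated pair therefore fits either test and does not identify which was powered. Because the residual variance is unstated, the mismatch under A is a failure to reproduce, not a proven error.

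**Formulas, with V = 4.84 (residual 2.77).** The noncentrality is λ = (46/2) × d′Σ⁻¹d.

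- Averaged level: variance 2.07 + 2.77/3 = 2.993; λ = 23 × 1.12²/2.993 = 9.64; power 86.7%.
- Averaged, adjusted for 0 h: adjustment removes ρ₀²V, where ρ₀ is the 0 h correlation. Here that is 2.07²/4.84 = 0.885, leaving 2.108; λ = 13.69; power 95.5%. At ρ₀ = 0.2 it removes 0.04 × 4.84 = 0.194; power 88.8%. At ρ₀ = 0 it removes nothing; power stays 86.7%.
- Joint arm-by-time (3 df): λ = 23 × [Σd² − (Σd)²/4]/2.77 = 23 × (3.8066 − 2.8224)/2.77 = 8.17; power 65.7%.
- 24 h minus 0 h: λ = 23 × 0.96²/(2 × 2.77) = 3.83; power 49.0%.
- Arm-by-time on 6, 12 and 24 h only: λ = 23 × [3.8066 − 3.36²/3]/2.77 = 0.36; power 7.8%.

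**Power (%) at N=92**

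| Test | V=4.84 | V=4.56 | V=4.00 | V=3.53 (B) |
|---|---|---|---|---|
| Averaged level, unadjusted | 86.7 | 87.7 | 89.7 | 91.3 |
| Averaged, adjusted for 0 h | 95.5 | 96.7 | 98.6 | 99.6 |
| Same, ρ₀ = 0.2 | 88.8 | 89.7 | 91.4 | 92.8 |
| Joint arm-by-time, 3 df | 65.7 | 70.9 | 82.5 | 92.1 |
| Same, ρ₀ = 0.2 | 45.5 | 47.5 | 52.3 | 57.2 |
| 24 h minus 0 h change | 49.0 | 53.2 | 64.0 | 75.9 |
| Arm-by-time on 6, 12, 24 h only | 7.8 | 8.1 | 9.0 | 10.4 |

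The last row shows that the powered F was probably not an interaction over the three post-baseline times alone. The text does not say whether it was an averaged arm effect or a test including 0 h.

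For the 6 h contrast alone, adjustment raises power from 77-88% to 85-97% across the four settings, and by 1-2 points at ρ₀ = 0.2.

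**Effect shape.** Take assumed differences of 1.25, 0.6 and 0 (mean 1.85/3 = 0.617) with V = 4.84.

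- Adjusted average: λ = 23 × 0.617²/2.108 = 4.15; power 52%.
- Joint arm-by-time: λ = 23 × (1.9225 − 1.85²/4)/2.77 = 8.86; power 70%.

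Under B these are 71% and 94%. The ranking seen with the plan's near-flat differences reverses.

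**The case against.** The best defence is that the plan can be read as a whole. Change is primary, level is separately secondary, the contrasts are there to estimate, and the parallel model for the other markers is introduced as a test of change. On that reading arm-by-time decides, and 0 h lactate is used unconditionally as a response. This is the natural reading and it narrows the gap. It does not close it: the primary section lacks that phrase, the parallel section does not say whether the joint term or a contrast decides, and the power section describes a difference over three times without 0 h.

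The size of the adjustment gain rests on a correlation that the plan does not give. Eligibility requires lactate of at least 3, which truncates the 0 h distribution and makes a correlation as high as that among later values uncertain. That stands, and it is why the gain is given as a range down to nil. Under B the joint and unadjusted averaged tests also nearly coincide (92% and 91%), so the gap between those two depends on unstated inputs.

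Three stronger inferences are tempting, and the document supports none of them.

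- That success at any single time would count, inflating the error rate. The plan states no such rule.
- That omitting 0 h lactate biases the comparison. Unadjusted comparisons in a randomised trial are unbiased.
- That the adjusted 6-24 h average is simply the right test. The plan expects the maximal effect at 6 h, and averaging does worse if the effect fades.

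**Conclusion.** The point holds in two limited parts.

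1. No test is named as deciding the primary outcome, and the passages that might settle it point in different directions. This does not depend on any variance assumption.
2. The named level contrasts leave 0 h lactate unused unless a significance-triggered rule brings it in. For the averaged difference at N=92, prespecified adjustment takes power from 87-91% to 96-99.6% at a 0 h correlation of 0.43-0.59, adds about 2 points at 0.2 and nothing at zero, where it costs essentially nothing.

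The figures assume compound symmetry, the plan's differences and no attrition. The joint arm-by-time figures (66-92%) also assume equal variance at 0 h; the adjusted figures do not depend on the 0 h variance. The matter is precision and pre-specification, not validity, and it should be settled before unblinding.

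**What to change.** 1. In the primary model, constrain the 0 h means to be equal across arms (or enter 0 h lactate as a covariate) whatever the observed balance. Exempt 0 h lactate from the significance-triggered rule in General Principles.
2. Name one deciding test from that model at two-sided 0.05. Report the 6, 12 and 24 h contrasts with 95% confidence intervals as supportive.
3. Restate power for that test, giving the residual variance and the 0 h assumptions.

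Two candidates fit the plan. The baseline-adjusted difference averaged over 6, 12 and 24 h matches the times that were powered; conditional on 0 h lactate, an arm difference in level is also an arm difference in change. A joint baseline-adjusted test over the three times is less exposed to a fading effect. With the plan's differences it has 89% (V = 4.84) or 92% (V = 4.56), against 96% and 97% for the adjusted average. The choice is the sponsor's.

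The cost is SAP wording and a rerun of the power calculation. No new data are needed, and the document says it precedes any data analysis. The secondary tests of absolute lactate can stay. If the average is chosen, a benefit confined to one time could not be claimed as primary success.

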Prior to unblinding or analysis, oxygen consumption data will be cleaned using an algorithm designed by our research team in R version 4.1.1 (R Foundation for Statistical Computing, Vienna, Austria). This automated algorithm excludes VO₂ data (and the corresponding value for carbon dioxide production, or VCO₂) if one or more of the following criteria is met: all values recorded in the 10 min following a change in FiO₂ of 10%, all values recorded while FiO₂ is >61% (61% used in order to capture all situations when the ventilator is set for an FiO₂ of 60% or less, as the monitor reports this number to two decimal places and a set number of 60% may be recorded as 60.54%), all values deviating 15% or more from the mean of the previous five values and the next five values (i.e, deviating 15% from the mean of the ten neighboring data points), and all VO₂ values out of physiologic range unless these are persistent for more than 30 minutes, as these measurements are considered artifacts. Values that will be considered out of physiologic range are VO₂<80 mL/kg/min or VO₂>800 mL/kg/min. We allow these values if they persist for at least 30 min and if they are not excluded per the algorithm for other reasons, as critically ill post-arrest patients can sometimes have values well outside of standard normal range, due to temperature, medication use such as sedatives and neuromuscular blockade and/or alterations in metabolic function. The respiratory quotient (RQ) is calculated as the ratio of VCO₂/VO₂ at each time point. After data is run through the algorithm and still prior to unblinding, there is a final visual review of a graphical print-out of all data points for each patient to provide a secondary confirmation that values were kept or dropped appropriately.

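### The VO₂ limits for excluding artifacts are printed in mL/kg/min, but the SAP treats the VO₂ series as not yet divided by body weight

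*SAP*

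**What the plan says.** All the relevant text is in the SAP, Analysis of Secondary Outcomes, under the heading on change in oxygen consumption (VO₂) over 48 hours.

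- **Cleaning.** An automated R algorithm applies four exclusion criteria before unblinding: two based on FiO₂, one based on a 15% deviation from neighbouring values, and a range check. The range check removes "all VO₂ values out of physiologic range unless these are persistent for more than 30 minutes, as these measurements are considered artifacts". The limits follow: "Values that will be considered out of physiologic range are VO₂<80 mL/kg/min or VO₂>800 mL/kg/min". When a VO₂ value is dropped, its VCO₂ value goes with it.
- **Exception.** Out-of-range values are kept if they last long enough and no other criterion excludes them: "We allow these values if they persist for at least 30 min".
- **Visual review.** A graphical check of every patient's data follows, still before unblinding, "to provide a secondary confirmation that values were kept or dropped appropriately".
- **Analysis.** Each AUC is divided by the minutes of data available. The VO₂ and VCO₂ AUCs "are influenced by the weight of the patient, and thus will also be adjusted by dividing by the bodyweight of the patient, in kilograms".

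The VO₂ monitoring paragraph under Protocol describes breath-by-breath recording but gives no unit. The only VO₂ unit in the document is the one attached to the two limits.

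**The concern.** The two statements do not fit together. A series already expressed per kilogram has no need of division by body weight. A series that does need it cannot be compared with per-kilogram limits unless the readings or the limits are first converted, and the SAP describes no such step.

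This is an operating threshold for removing data, not background text. VO₂ is the first secondary outcome listed. Because the paired VCO₂ value is dropped too, the rule also determines which readings enter VCO₂, RQ and the VO₂:Lactate ratio, as well as the planned VO₂ subanalyses. The document was posted before any data analysis as a public specification, and anyone who tries to reproduce the cleaning from it will meet a rule that does not match the data it describes.

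**Working it through.** **Inputs from the SAP**

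- Limits as printed: 80 and 800 mL/kg/min.
- Adjustment of the VO₂ AUC: divide by minutes of data, then by body weight in kg.

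**Inputs assumed, because the SAP gives neither**

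- Body weight 40 to 150 kg, with 70 kg as the working example.
- Genuine VO₂ of 2 to 8 mL/kg/min in these patients.

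No sample size, power or alpha figure depends on this point, so there is no figure in the plan to reproduce. The check is one of units.

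**Step 1: which unit makes the analysis coherent?**

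- Series in mL/min: AUC is (mL/min) × min = mL. Dividing by minutes and by kg gives mL/kg/min, an ordinary weight-indexed rate.
- Series in mL/kg/min: AUC is mL/kg. Dividing by minutes and by kg gives mL/kg²/min, which is not a meaningful quantity.

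The analysis text is coherent only if the series is in mL/min.

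**Step 2: the printed limits on the scale of that series**

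Limit in mL/min = limit in mL/kg/min × weight.

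| Assumed weight | Lower limit | Upper limit |
|---|---|---|
| 40 kg | 80 × 40 = 3,200 mL/min | 800 × 40 = 32,000 mL/min |
| 70 kg | 80 × 70 = 5,600 mL/min | 800 × 70 = 56,000 mL/min |
| 150 kg | 80 × 150 = 12,000 mL/min | 800 × 150 = 120,000 mL/min |

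**Step 3: the same numbers read as mL/min**

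Limit in mL/kg/min = limit in mL/min ÷ weight.

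| Assumed weight | Lower limit | Upper limit |
|---|---|---|
| 40 kg | 80/40 = 2.0 mL/kg/min | 800/40 = 20.0 mL/kg/min |
| 70 kg | 80/70 = 1.14 mL/kg/min | 800/70 = 11.43 mL/kg/min |
| 150 kg | 80/150 = 0.53 mL/kg/min | 800/150 = 5.33 mL/kg/min |

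The two interpretations differ by a factor equal to body weight: 70-fold at 70 kg.

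**Step 4: the printed limits taken literally**

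The top of the assumed genuine range, 8 mL/kg/min, is 8/80 = one tenth of the printed lower limit, whatever the patient's weight. Every genuine reading would therefore be flagged as too low. The exception for persistent values, which the SAP presents as covering patients who sometimes fall outside the normal range, would then apply to every patient all the time. As far as this criterion is concerned, a reading would be kept or dropped according to how long the run containing it lasted, not according to whether it was an artifact.

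**The case against.** The strongest reply is that this is a printing slip with no consequence. The later text on weight adjustment settles that the data are unindexed, so the obvious meaning is 80 and 800 mL/min. A script that compares raw mL/min with those numbers does what was intended. Cleaning is blinded, three other automated criteria remain, and a limit that flagged nearly everything should be conspicuous at the visual review. Most of this stands, and it is why the point is rated low. It does not remove the point: the stated rule is still wrong, the script is not available to the reader, and the visual review is described only as a secondary confirmation of what was kept or dropped.

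Two stronger readings are tempting but not supported.

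- A reader might infer that VO₂ is already per kilogram and is then divided by weight a second time. The SAP says the AUC is still influenced by weight, and it states one division by weight, at the AUC step. That contradicts the inference.
- A reader might infer that genuine data will be lost from patients with short recordings, because the AUC is "influenced by the number of minutes of data available, which varies between patients". Variation in total minutes does not show that continuous runs are shorter than 30 minutes. Recording may extend over 48 hours, and in longer runs even the literal rule removes nothing, because the persistence exception keeps the values.

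**Conclusion.** The point holds as an internal inconsistency of units. The printed exclusion limits are on the wrong scale for the series that the SAP goes on to analyse, by a factor equal to body weight (at an assumed 70 kg, 5,600 to 56,000 mL/min where 80 to 800 mL/min is coherent with the analysis text). The mismatch itself rests on the document alone. The illustrative figures rest on assumed body weights, and the statement that essentially every reading would be flagged rests on an assumed VO₂ range of 2 to 8 mL/kg/min.

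The consequence depends on code that cannot be seen. Most likely it is nil, because reading the unit as a slip for mL/min requires no step that the SAP does not describe. If the script does follow the text, the range check no longer separates artifact from genuine readings, and VO₂, VCO₂, RQ and the VO₂:Lactate ratio are exposed. Even then, blinded cleaning means that an error should not favour an arm, and the primary lactate outcome and the sample size are untouched. The document does not support a claim that data have been or will be lost. Low severity.

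**What to change.** Reconcile the cleaning paragraph with the weight-adjustment paragraph. State the limits in the unit of the data being cleaned (VO₂ below 80 mL/min or above 800 mL/min is the version coherent with the later text), and say that they are applied before the single division by body weight already described at the AUC step. Before unblinding, confirm that the R cleaning script uses that unit.

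The cost is a one-line correction to the SAP and a short check of the script. No new data are needed and the primary analysis does not change.
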